2 RESEARCH QUESTIONS AND OBJECTIVES

This surveillance study aims to establish active surveillance for hospitalised SARI cases in adults in Europe.

2.1 Primary objectives

- 1 To calculate the proportion of laboratory samples positive for each viral respiratory pathogen of interest¹, among adult patients hospitalised with SARI;
- 2 To characterise adult SARI patients (including age, gender, protective- and risk factors, specific treatments, and healthcare utilisation outcomes), overall and by viral respiratory pathogen of interest¹.

2.2 Secondary objectives

3 To investigate the prevalence of co-infection with the viral respiratory pathogens of interest¹, in adult patients hospitalised with SARI, and the impact on healthcare utilisation outcomes².

2.3 Exploratory objectives

- 4 To calculate pathogen-specific SARI incidences and describe trends in hospitalised adults (time period, country, level of severity);
- 5. To perform feasibility assessments for future respiratory disease studies within the id.DRIVE Study Network (e.g., effectiveness studies, impact studies).

² Healthcare utilisation outcomes are defined by outcome (hospitalisation without ICU admission or in-hospital death; ICU admission without in-hospital death; in-hospital death), by the need for respiratory support (none; non-invasive ventilation; mechanical ventilation; ECMO), discharge destination and length of stay.

Confidential

¹ SARS-CoV-2 and/or SARS-CoV-2 specific variant, Influenza A/B, Respiratory Syncytial Virus (RSV) A/B, Adenovirus, Parainfluenza viruses (1-4), human metapneumovirus (hMPV), human rhinovirus (HRV), human enterovirus (HEV), human coronaviruses (229E/NL63/OC43/HKU1)

3 RESEARCH METHODS

3.1 Study design

This study is a non-interventional multi-country, multi-centre, hospital-based surveillance study of viral respiratory pathogens in adults hospitalised for SARI.

A combination of primary (e.g., lab results) and secondary data collection (e.g., vaccination registries) will be used to obtain the relevant data.

3.2 Study Contributors (study sites)

This is a multi-country, multi-centre study, with hospital sites in Europe. The participating Study Contributors (also referred to as study sites) are described in Table 1. Additional countries, and or Study Contributors may be included during the study period.

The participating Study Contributors are either individual hospitals or hospital networks. The data collection will be a prospective data collection from primary and secondary data sources, and in some sites, data will additionally be retrieved from the existing hospital databases and linked data.

		Number of	No. of hospital	Recruitment
Country	Study Contributor ¹	hospitals	beds/ICU beds	wards
Spain	VAHNSI	5 hospitals	3347/143	ED
	GTPUH	1 hospital	794/95	All, through
				hospital records
	HUVH	1 hospital	1154/56	All, through
	_			hospital records
	Hospital Clínic de	1 hospital	767/63	ED
	Barcelona			
	Hospital Clínico	1 hospital	1511/38	All, through
	Universitario de			hospital records
	Santiago de			
	Compostela			
	Hospital	1 hospital	1308/31	Through hospital
	Universitario La Paz			records
Italy	CIRI-IT	6 hospitals	5623/281	ED
	Luigi Sacco Hospital	1 hospital	507/20	ED
Belgium	UZA	1 hospital	605/45	ED
	St. Pierre	1 hospital	600/32	Infectious diseases

Table 1. Participating Study Contributors.

Germany	Univeritätsklinikum	1 hospital	1000/30	Infectious diseases
	Ulm			
	Universitätsklinikum	1 hospital	1250/96	ED
	Frankfurt			
	Universitätsklinikum	1 hospital	2180/48	ED and hospital
	Freiburg			records

Abbreviations: ICU, intensive care unit; GTPUH, German Trias I Pujol University Hospital; HUVH, Vall d'Hebron University Hospital; CIRI-IT, Centro Interuniversitario per la Ricerca sull'Influenza – Italy; UZA, University Hospital Antwerp; ED, emergency department

¹Study Contributor selection may differ by Study Requestor

3.3 Study population

The study population consists of adults aged 18 years and older (patients), presenting at the participating hospitals during the study period, who

- meet the inclusion criteria (see Section 3.3.1) AND
- are hospitalised and meet the SARI case definition (see Section 3.6.2).

Participants may be co-enrolled in interventional trials. The name of the trial will be collected, to allow for exclusion from specific analysis, where required, and will be prespecified in the statistical analysis plan (SAP).

3.3.1 Inclusion criteria

Individuals (patients) that meet the study population criteria need to fulfil the following inclusion criterion:

• Willing and able to provide informed consent, when applicable, obtained from the patient or from the patient's legally acceptable representative(s) (LAR).

3.3.2 Exclusion criteria

No exclusion criteria have been defined.

3.4 Study period

From June 2024, with a minimum duration of 12 months and an expected duration of two years. A graphical visualisation of the study timelines is provided in the figure below (Figure 1):

Figure 1: Study timelines

3.5 Study outcomes

The outcome of interest for the primary objectives will be **laboratory-confirmed infection** (Section 3.6.3) with one of the viral respiratory pathogens of interest (see section 3.8.1) in patients hospitalised with SARI symptoms, and laboratory-confirmed co-infection (section 3.6.4) for the secondary objective.

For the second secondary objectives, healthcare utilisation outcomes of interest are:

- Level of severity (Section 3.6.5.1).
- Discharge destination (Section 3.6.5.2)
- Length of stay (section 3.6.5.3)

Pathogen-specific SARI incidences will be calculated to address the first exploratory objective (see section 3.13.5). The denominator will be based on the sum of the catchment populations covered by the Study Contributors [26].

For the second exploratory objective, **feasibility assessments** for future respiratory disease impact and effectiveness studies will be made as described in Section 3.13.6.

3.6 Definitions

3.6.1 Hospitalised patient

Persons admitted to the hospital with overnight stay. An overnight stay is defined as at least one day difference between date of presentation at the hospital and discharge date. In case of referral to

Confidential Version 1.0

21 March 2024 Page **25** of **49** another hospital, the date of hospital admission is defined as the date of first admission (i.e., admission to the referring hospital).

3.6.2 SARI patient

A SARI patient is defined as a **hospitalised person** with a suspicion of a respiratory infection with **at least one** of the following symptoms:

- cough
- fever (≥ 38 C°)
- shortness of breath
- sudden onset of anosmia, ageusia or dysgeusia

with **symptom onset within the last 14 days** prior to hospital admission. This SARI definition is modified from the latest ECDC case definition (specifying "suspicion of respiratory infection") [23].

3.6.3 Laboratory-confirmed infection

For each studied pathogen, a laboratory-confirmed infection is a positive reverse transcription polymerase chain reaction (RT-PCR)³ or multiplex RT-PCR on a respiratory specimen(s) collected between 14 days prior to and up to 72 hours after hospital admission. If all samples collected in this time frame are negative, the patient is considered as not having any laboratory-confirmed infection.

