Hospitalised person: SARI patients will be identified among patients admitted to the hospital with at least one overnight stay.

Laboratory-confirmed infection: For each studied pathogen, a laboratory-confirmed infection is defined as a positive reverse transcription polymerase chain reaction (RT-PCR)³ or multiplex RT-PCR on any respiratory specimen(s) collected between 14 days prior to and up to 72 hours after hospital admission. The absence of a laboratory-confirmed infection requires all samples collected in this time frame to be negative.

³ Or another RNA amplification system with at least the same sensitivity as RT-PCR (e.g., transcription-mediated amplification (TMA)).

Confidential Version 1.0 21 March 2024 Page **13** of **49** Laboratory-confirmed co-infection: Laboratory-confirmed co-infection is defined as two or more laboratory-confirmed infections on any respiratory sample collected between 14 days prior to and up to 72 hours after hospital admission.

Laboratory testing

Clinical specimens will be taken from all SARI patients included in the study (within 72 hours after hospital admission). The preferred respiratory specimen is a nasopharyngeal swab. Additional respiratory specimens are accepted (e.g., nasal swab, oropharyngeal swab, bronchoalveolar lavage, aspirates). Sample type will be recorded.

The specimens will be tested for at least SARS-CoV-2, influenza A/B and respiratory syncytial virus (RSV) A/B, and preferably also for adenovirus, parainfluenza 1-4, human metapneumovirus (hMPV), human rhinovirus (HRV), human enterovirus (HEV), and human coronaviruses (229E/NL63/OC43/HKU1), by using validated RT-PCR or multiplex RT-PCR assays, or another RNA amplification system with at least the same sensitivity as RT-PCR (e.g., transcription-mediated amplification (TMA)).

Further genotyping or subtyping, if not available through local multiplex, will be performed on specimens that test-positive for:

- RSV:
 - Subtype A and B
- Influenza:
 - Type A and B
 - Subtypes A H1, Influenza A H3
- SARS-CoV-2:
 - Genotyping (pangolin lineage)

Covariates

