3.6.4 Laboratory-confirmed co-infection

Laboratory-confirmed co-infection is defined as two or more laboratory-confirmed infections (Section 3.6.3) on any respiratory sample taken in the accepted timeframe (collected between 14 days prior to and up to 72 hours after hospital admission).

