3.8 Pathogens of interest and laboratory testing

3.8.1 Pathogens of interest

The pathogens of interest are as follows:

- Severe Acute Respiratory Syndrome Coronavirus-2 (SARS-CoV-2)
- Influenza
 - Influenza A
 - A-H1
 - A-H3
 - o Influenza B
- Respiratory Syncytial Virus (RSV)
 - RSV A and RSV B
- Parainfluenza
 - Type 1-4
- Human Metapneumovirus (hMPV)
- Human Rhinovirus (HRV)
- Human Enterovirus (HEV)
- Adenovirus
- Human coronavirus
 - Types 229E, NL63, OC43 and HKU1

At minimum, sites should have testing capacity for SARS-CoV-2, Influenza A and B, and RSV A and B. Additional pathogens may be added to the study depending on epidemiological trends (e.g., inclusion of an emerging pathogen).

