3.8.2 Laboratory testing

To the extent possible, clinical specimens will be collected from the patients eligible for the study as part of routine clinical sampling for diagnostic work-up. However, depending on local practice, additional sampling for the purpose of the study may be required. Samples collected between 14 days prior to and up to 72 hours after admission are accepted. Nasopharyngeal or oropharyngeal swabs are recommended. Additional respiratory specimens are accepted (e.g., nasal swabs, oropharyngeal swab, saliva, mouth wash, bronchoalveolar lavage, aspirates). Sample type will be recorded.

The specimens will be tested within the local laboratory infrastructures of the participating Study Contributors, for at least SARS-CoV-2, influenza A/B and RSV A/B, and preferably also for adenovirus,

Confidential Version 1.0 21 March 2024 Page **28** of **49** Parainfluenza 1-4, human metapneumovirus (hMPV), human rhinovirus (HRV), human enterovirus (HEV), and human coronaviruses (229E/NL63/OC43/HKU1), by using validated RT-PCR or multiplex RT-PCR assays, or another RNA amplification system with at least the same sensitivity as RT-PCR (e.g., transcription-mediated amplification (TMA)). Assays used are either commercial assays with known high sensitivity, specificity and/or concordance, or in-house developed assays that have undergone quality and/or validation processes. Study Contributors will be requested to submit validation logs (summarising the quality check process, results, timing and certificates of analysis for assays performed) to the Study Team.

			Number of pathogens
Study Contributor, Country	Brand	Panel	tested
VAHNSI,	In-house	In-house	20
Spain			
Val d'Hebron,	SeeGene	Allplex RP 1-3	19
Spain	Cepheid GeneExpert	Xpert [®] Xpress CoV-	4
		2/FLU/RSV plus	
GHTiP,	SeeGene	Allplex SARS-CoV-	4
Spain		2/FLU/RSV	19
		Allplex RP 1-3	
Hospital Clínico Universitario de	BioFire	FilmArray	18
Santiago de Compostela,			
Spain			
Hospital Clínic de Barcelona,	GeneXpert	ТВС	
Spain			
Hospital Universitario La Paz,	BioFire	ТВС	
Spain	Cepheid GeneXpert		
CIRI-IT,	SeeGene (Bari, Genoa)	Allplex RP 1-3	19
Italy	In-house (Milan)		
	TBC (Sienna, Pisa)		
Luigi Sacco Hospital,	SeeGene	Allplex RP	21
Italy			
UZA,	Pathofinder	Respifinder 2smart	18
Belgium			
St Pierre,	Qiagen Qiastat	RP SARS-CoV-2	18
Belgium	Abbott Alinity m RESP		4
	4-plex TaqMan	In-house	17
Universitäts-klinikum Frankfurt,	SeeGene	Allplex RP 1-3	19
Germany	BioFire	FilmArray RP2.1	18

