Universitäts-klinikum Ulm,	SeeGene / GeneXpert	ТВС	
Germany			

Table 2. Multiplex assays (brand, panel, and number of pathogens) used by Study Contributors

Study Contributor, Country	Brand	Panel	Number of pathogens tested
Universitäts-klinikum Freiburg,	Pathofinder	Respifinder 2smart	18
Germany			

*CIRI-IT location Rome does not use multiplex yet, but is considering implementation of SeeGene Allplex or Roche ePlex (to be finalised in June 2024); TBC, to be confirmed

Further genotyping or subtyping will be performed on specimens that test-positive for:

- RSV:
 - Subtype A and B (if not available through local multiplex)
- Influenza:
 - Type A and B (if not available through local multiplex)
 - Subtypes A H1, Influenza A H3 (if not available through local multiplex)
- SARS-CoV-2:
 - Genotyping (pangolin lineage)

Genomic sequencing will be performed by whole genome sequencing or next generation sequencing using commercially available molecular kits. Sites will be requested to communicate to the Study Team the sequencing methodology applied, software version used, and the references of the laboratory performing the test.

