3.13.2 Total SARI and pathogen-specific SARI numbers

The total number and proportion of positive laboratory samples for each respiratory pathogen of interest (see section 3.8.1) and co-infections (see section 3.6.4) will be provided. Counts and proportions (%, along with 95% exact binomial confidence intervals) will be provided by calendar time, by Study Contributor, by country and by age- and risk groups of interest. Co-infections (%) will be described, by number of pathogens, by pathogen type and by healthcare utilisation outcomes. Visualisations of these counts and percentages over time will be provided.

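### Infection status and co-infection are defined without regard to which viruses were tested, so the co-infection objective depends on panel breadth

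*Protocol*

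**What the plan says.** Section 3.6.3 defines a positive separately for each pathogen, then gives a patient-level rule for the negative: "If all samples collected in this time frame are negative, the patient is considered as not having any laboratory-confirmed infection". The abstract has the same rule: "The absence of a laboratory-confirmed infection requires all samples collected in this time frame to be negative". Neither names the viruses that must have been tested, and neither has a category for a virus that was not tested.

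Co-infection (section 3.6.4) is "two or more laboratory-confirmed infections (Section 3.6.3) on any respiratory sample taken in the accepted timeframe", with no minimum panel. Section 3.13.2 adds: "Co-infections (%) will be described, by number of pathogens, by pathogen type and by healthcare utilisation outcomes". Objective 3 is the prevalence of co-infection and its impact on healthcare utilisation.

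The required test set is narrower than the list of pathogens of interest. Section 3.8.1: "At minimum, sites should have testing capacity for SARS-CoV-2, Influenza A and B, and RSV A and B". Section 3.8.2 has specimens tested "for at least SARS-CoV-2, influenza A/B and RSV A/B, and preferably also for adenovirus", and continues that preference to parainfluenza, hMPV, rhinovirus, enterovirus and the seasonal coronaviruses. Three virus groups are thus mandatory and six optional, although all nine are pathogens of interest for objectives 1 to 3.

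Table 2 lists confirmed panels of 4 to 21 targets. Several entries are still to be confirmed, and a footnote says: "CIRI-IT location Rome does not use multiplex yet".

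**The concern.** A patient tested only for the core viruses and a patient tested for all nine groups get the same label when everything run is negative. The label means something different in each case, and the definitions do not separate them.

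The clearest consequence is for objective 3. A core-only patient cannot show any co-infection that involves an optional virus, so the count rises with the number of targets run. The risk factors named in section 3.13.4 (age, gender, chronic conditions, smoking) do not include panel. If sites differ both in panel and in outcomes such as ICU admission or length of stay, part of any link between co-infection and outcome reflects panel. The direction cannot be told from the protocol.

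The second consequence is conditional. If untested patients entered the denominator as negatives, positivity for the six optional groups (objective 1) would be too low and not comparable between sites. Incidence under section 3.13.5, which multiplies percent positive by all SARI patients, would inherit the error. Reports are Requestor-specific with their own site selections (section 8.3), so panel mix could also differ between reports of one study.

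**Working it through.** **1. The plan's own figures.** The hospitals in Table 1 sum to 22. 22 × 300 = 6,600, and 6,600 × 0.9 = 5,940, as section 3.10 states. The half-width of the exact 95% interval at n = 5,940 (lower limit from Beta(x, n − x + 1), upper from Beta(x + 1, n − x)) is 1.025% at 20%, 1.109% at 25%, 0.365% at 2%, 0.657% at 7% and 0.835% at 12%. All agree with Table 4, which covers only the three mandatory viruses.

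**2. Panels by hospital.** Table 2 mapped to Table 1, taking each of the six CIRI-IT locations as one hospital:

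| Panels listed | Hospitals | Number |
|---|---|---|
| Extended only | VAHNSI 5, Santiago 1, Bari and Genoa 2, the other Italian contributor 1, UZA 1, Frankfurt 1, Freiburg 1 | 12 |
| 4-target and 17-19-target | HUVH, GTPUH, St. Pierre | 3 |
| Unconfirmed, unspecified or no multiplex yet | Clínic de Barcelona, La Paz, Milan, Siena, Pisa, Rome, Ulm | 7 |

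The total is 22. Table 2 counts targets without naming the viruses, so I assume that an extended panel covers all six optional groups.

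**3. Co-infection by panel, same patients.** With independent detections of probability p for each group:
- P(none) = Π(1 − p)
- P(exactly one) = P(none) × Σ p/(1 − p)
- P(co-infection) = 1 − P(none) − P(exactly one)

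Core panel, Table 4 minimum rates (20%, 2%, 7%): P(none) = 0.80 × 0.98 × 0.93 = 0.7291. P(exactly one) = 0.7291 × (0.2500 + 0.0204 + 0.0753) = 0.2520. Co-infection = 0.0188, or 1.9%.

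The wide panel adds six groups. The protocol gives no prevalence for them, so I assume 1% to 3% each:

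| Core rates | Core panel | Wide panel, optional groups at 1% / 2% / 3% |
|---|---|---|
| Table 4 minimum | 1.9% | 3.5% / 5.2% / 7.0% |
| Table 4 maximum (25%, 7%, 12%) | 5.2% | 7.2% / 9.3% / 11.5% |

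The ratio of wide to core runs from 7.22/5.17 = 1.4 to 7.00/1.88 = 3.7.

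**4. Dilution of an optional virus, if the untested were counted as negative.** Observed = true prevalence × share tested. With equal recruitment, each hospital contributes 300 × 0.9 = 270 patients.
- 12 hospitals: 12 × 270 = 3,240; 3,240/5,940 = 55%.
- 15 hospitals: 15 × 270 = 4,050; 4,050/5,940 = 68%.

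| True prevalence (assumed) | 55% tested | 68% tested | 90% tested | All tested |
|---|---|---|---|---|
| 6% | 3.3% | 4.1% | 5.4% | 6.0% |
| 10% | 5.5% | 6.8% | 9.0% | 10.0% |

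The 55% column is a worst case: it takes the dual-panel hospitals and all seven open ones as testing no optional virus. A tested-for denominator removes this arithmetic dilution in every column.

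**5. Cost of restricting to confirmed extended panels.** The interval width ratio is √(5,940/3,240) = 1.35.

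**The case against.** The definition opens pathogen by pathogen, and a patient negative on four targets does, literally, have no laboratory-confirmed infection. Objective 1 and section 3.13.2 concern samples positive for each pathogen, and the natural denominator is samples tested for that pathogen. The SAP can say so, the assay used is among the minimum data collected, and results are reported by Study Contributor and country.

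Much of this stands. A reader might infer that untested patients are counted as negative for each virus; no passage says so. A reader might also take Table 2 to mean that some sites test only four targets, but every confirmed 4-target assay sits beside a 17-19-target one. Several open sites may prove wide: La Paz lists BioFire, which has 18 targets elsewhere in Table 2, Ulm lists SeeGene, which has 19-target panels elsewhere, and Rome's choice was due in June 2024.

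Two further inferences are tempting and unsupported. The protocol does not say which patients get which panel, so a wider panel for sicker patients is only a possibility. It also defines no test-negative comparison group; effectiveness studies are future work (section 3.13.6).

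The objection does not reach the definitions. The negative rule covers any infection and omits a tested-for condition, and co-infection has no minimum panel. These are fixed in the protocol, not deferred as risk groups and incidence details are. The limitations (section 5) answer assay differences with sensitivity, specificity and validation, and do not mention panel breadth.

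**Conclusion.** The point holds for the definitions and for objective 3, and should be fixed. Followed as written, co-infection prevalence depends on panel breadth, by a factor of about 1.4 to 3.7 between a core-only and a wide panel. That range rests on Table 4 rates, an assumed 1-3% for each optional group, and independent detections. The effect on the pooled estimate would be smaller and depends on the share of patients on each panel, which the protocol does not give. The association of co-infection with healthcare outcomes is open to the same influence, in an unknown direction.

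For positivity of the six optional groups the finding is conditional: the protocol leaves the denominator open, and the loss runs from nearly half in the worst case to almost nothing if nearly all patients are tested. Positivity for SARS-CoV-2, influenza and RSV, the sample size and Table 4 are largely unaffected.

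**What to change.** - Section 3.6.3 and abstract: define status per pathogen as positive, negative (tested for that pathogen and all in-window results negative) or not tested.
- Sections 3.13.2 and 3.13.5: use patients tested for the pathogen as the denominator of its percent positive, and report how many were tested.
- Sections 3.6.4 and 3.13.4: run the main co-infection analysis in patients tested for a common full panel, report co-infection among the three core viruses for everyone, and stratify or adjust the outcome models by panel.
- Section 5: name panel breadth as a limit on comparability.

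This is mainly a change of wording, since the assay used is already recorded; panels listed as unconfirmed need mapping to viruses. The price is a smaller full-panel analysis: 3,240 patients if only the 12 confirmed hospitals qualify, with intervals up to about 1.35 times wider, and less if the other sites confirm wide panels. The restricted set may also represent the network less well, so the core-virus result for everyone should stand beside it.
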